6.2. Study Assessments

6.2.1. Tumor Biopsy

Timing of biopsies are as follows:

- Part A (all subjects except backfill subjects): 3 sequential tumor biopsies are mandated; one biopsy at baseline, the second biopsy prior to the initiation of the combination therapy (after 2 weeks) and the third biopsy after the first cycle of combination treatment (either at the End of Treatment Visit or, if combination treatment is continued, at the end of Cycle 2/beginning of Cycle 3). These biopsies are mandatory in order to assess immune cell infiltration in the tumor

Part A (backfill subjects): 2 serial tumor biopsies are mandated; one biopsy at baseline and a second biopsy after 4 weeks of combination treatment (either at the End of Treatment Visit or, if combination treatment is continued, at the end of Cycle 2/beginning of Cycle 3).

For all Part A subjects: in case a tumor biopsy is non-evaluable, an optional biopsy can be collected at the next medically feasible timepoint during ongoing treatment and as per treating physician's decision to assure assessable histology data

- Part B: Baseline biopsies are mandatory in all subjects; for melanoma, cutaneous squamous-cell carcinoma and the biomarker cohort with mixed solid tumors ("basket" cohort), an additional on-treatment biopsy after the first 8 weeks (for cutaneous squamous-cell carcinoma: 9 weeks) of treatment (dependent on dosing scheme i.e., combination with nivolumab after 4 cycles [8 weeks] and with cemiplimab after 3 cycles [9 weeks]) is mandatory. In case the second biopsy is non-evaluable, an optional third biopsy can be collected if seen as safe and feasible at the next possible timepoint during ongoing treatment and as per treating physician's decision.

Note: In case of initiation of stereotactic radiotherapy in addition to study treatment, an optional tumor biopsy should be performed no earlier than 4 weeks after initiation of radiotherapy, again only if seen as safe and medically feasible by the treating physician, as in all biopsy cases.

- For subjects enrolled under this version of the protocol and under previous protocols v4.0 and v5.0: an optional retrospective analysis of PD-L1 and other relevant biomarkers might be conducted on archival tumor tissue any time after Screening provided the available material is < 120 days old and that the subject agrees in writing to this testing.
- For cutaneous squamous-cell carcinoma subjects: will be taken at a single timepoint (as per clinical possibility, ideally 3-5), as extensive molecular analyses are pursued (messenger ribonucleic acid [mRNA] expression analyses, such as T cell clonality analyses, RNAseq, nanostring analyses or genome sequencing etc.).

There has to be a lesion that is amenable to sequential biopsy, if possible, or a lesion in close proximity, but this lesion should ideally not be the only target lesion that will be radiologically assessed during the course of the study. If a sequential biopsy cannot be taken for safety reasons, this must be discussed with the Medical Monitor.

If stereotactic radiotherapy is initiated, another follow-up biopsy after 4 wks of the initiation of radiotherapy should be performed. **Note:** All biopsies are to be performed only if seen as safe and feasible from treating physician's discretion. Biomarkers may be analyzed from biopsy tumor tissue samples. Additional immune cell markers and/or tumor markers specific to any of the tumor type may be included.

Biopsied tumor tissue will be fixed with formalin and embedded in paraffin (formalin-fixed paraffin-embedded [FFPE]) to determine treatment-induced changes in the number, frequency and spatial location of infiltrating immune cells including but are not limited to leukocytes, different lymphocytes (e.g., CD4+ and CD8+ T cells, B cells, natural killer cells) by histology before and after treatment with CTL-002 or in combination with the defined checkpoint inhibitor. Moreover, the expression of the CTL-002 drug target, GDF-15 protein and mRNA, will be determined.

Retrospective exploratory analysis of, but not limited to additional immune cell characterization, gene expression, tumor mutational burden (TMB), microsatellite instability (MSI), indication-specific molecular signatures and other biomarkers will be optionally performed from FFPE tissue biopsies to support pharmacodynamic studies and confirm proof of mechanism.

Retrospective biomarker testing to address emergent questions will be not described elsewhere in the protocol (as part of the main trial) and will only be conducted on specimens from appropriately consented subjects. Retrospective biomarker studies will be conducted with appropriate biostatistical design and analysis and compared to PK/pharmacodynamic results, previously assessed biomarkers or clinical outcomes.

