1.10. Trial Endpoints

1.10.1. Primary Endpoints

Part A (Phase 1; dose escalation):

- Evaluation of the number of subjects with AEs, including serious adverse events (SAEs), clinical laboratory data, vital signs, electrocardiograms (ECGs), physical examination (including neurological assessment) and Eastern Cooperative Oncology Group (ECOG) performance status

Determination of DLTs and maximum tolerated dose (MTD) in Part A of the study using the National Cancer Institute Common Terminology Criteria for Adverse Events (NCI-CTCAE) Version 5.0

Part B (Phase 2a; expansion):

- Evaluation of the clinical efficacy according to Response Evaluation Criteria in Solid Tumors (RECIST) V1.1 of CTL-002 in combination with an anti-PD-1 checkpoint inhibitor by assessment of:
 - The proportion of subjects with tumor shrinkage, a confirmed partial response (PR) and/or complete response (CR), and overall response rate (ORR)
 - The interval between the date of first CTL-002 administration and first documented evidence of a PR or CR (time to response [TTR])
 - The interval between the date of first documented evidence of PR or CR, until first documented evidence of disease progression or death, due to any cause (duration of response [DOR])
 - The interval between the date of first CTL-002 administration and the earliest date of disease progression or death (progression free survival [PFS])
 - The interval between the date of first CTL-002 administration and date of death due to any cause (overall survival [OS])
- Evaluation of the number of subjects with AEs, including SAEs, clinical laboratory data, vital signs, ECGs, physical examination (including neurological assessment), and ECOG performance status

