5. Ability to understand the purpose of the study, provide signed and dated informed consent prior to performing any protocol-related procedures (including Screening evaluations), and able to comply with the study procedures and any locally required authorization.
6. For Part A, ideally ~50% of subjects enrolled per dose level should have increased GDF-15 serum levels (based on pre-screening result or historic serum GDF-15 data [up to 2 months prior to the start of treatment with CTL-002 where available]).
7. All subjects must have biopsy-accessible tumor lesions and be willing to undergo tumor biopsy: triple sequential biopsies (Part A) or dual-sequential biopsies (Part A backfill); in Part B, baseline biopsy (new or archived if obtained within 120 days prior to treatment start) from all subjects. For melanoma, cutaneous squamous-cell carcinoma and the biomarker cohort with mixed solid tumors (“basket” cohort) an additional on-treatment biopsy is mandatory. All biopsies are mandatory unless not seen as safe and feasible by the treating physician or another specific reason that precludes a biopsy sample being taken and which should be discussed with the Medical Monitor prior to Screening or if applying to the sequential biopsy, prior to that biopsy. All other study eligibility criteria must be met before the baseline biopsy sample is obtained.
8. For Part B, presence of radiologically measurable disease at baseline – with at least 1 lesion, not previously irradiated, that can be accurately measured at baseline as ≥ 10 mm in the longest diameter with computed tomography (CT) or magnetic resonance imaging (MRI) and is suitable for accurate, repeated measurements as per RECIST V1.1/iRECIST is required. This shall not be the lesion that is going to be biopsied.
9. ECOG Performance Status 0-1.
10. Life expectancy >3 months as assessed by the Investigator.
11. Adequate organ function:
 - a. Bone marrow function: hemoglobin ≥ 9.0 g/dL (equal to 5.59 mmol/L); platelet count $\geq 100 \times 10^9$ /L; leukocyte count $\geq 2.5 \times 10^9$ /L.
 - b. Hepatic function: AST and ALT $\leq 2 \times$ upper limit of normal (ULN) ($3 \times$ ULN in the case of liver metastases); bilirubin $\leq 1.5 \times$ ULN ($2 \times$ ULN in case of liver metastases/subjects with Gilbert’s disease).
 - c. Renal function: serum creatinine $< 1.5 \times$ ULN and/or creatinine clearance ≥ 50 ml/min (Cockcroft-Gault equation).

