6.2.5. Efficacy Assessment

6.2.5.1. Tumor Assessments (CT/MRI/PET-Scan, local Testing)

Tumor response is evaluated according to institutional standards using RECIST V1.1 as well as iRECIST criteria (refer to [Appendix 2](#)). For the purposes of this study, subjects will undergo evaluation at Screening for a baseline scan and should be re-evaluated every 8 weeks (6-9 weeks for the cutaneous squamous-cell carcinoma cohort only) and/or from the End of Treatment Visit, then after this time response assessments may be performed as per local institutional guidelines until the end of the Efficacy and Survival Follow-up. Refer to the SoAs in [Table 5](#), [Table 6](#) and [Table 7](#).

All lesions identified at Screening/baseline will be consistently followed using the unique lesion number assigned at Screening/baseline and need to be documented in the subject file and in the eCRF. Lesions that are being biopsied should not be included in the RECIST assessment.

The same method of assessment (imaging modality, e.g., MRI, CT) must be used to characterize each identified and reported lesion at baseline and during all follow-up examinations for an individual subject. If there is a change in modality, then the trial site may be asked to explain the reason for the change in the eCRF. A change in modality may be considered a protocol deviation.

Each efficacy time point/visit may be completed up to a window of ± 7 days in the Core Study Period and a window of ± 2 weeks in the Efficacy and Survival Follow-up period.

A central reading of the images by a reading center will be performed post-hoc in addition to local reading by the Investigator during the trial.

Definition of Progressive Disease according to RECIST V1.1 and iRECIST:

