where known residual benign tumors can remain). When effusions are known to be a potential adverse effect of treatment (e.g., with certain taxane compounds or angiogenesis inhibitors), the cytological confirmation of the neoplastic origin of any effusion that appears or worsens during treatment when the measurable tumor has met criteria for response or SD is advised to differentiate between response or SD and PD.

A 1.3 Tumor Response Evaluation

All subjects will have their BEST RESPONSE from the start of study treatment until the end of treatment classified as outlined below. Refer to [Table 11](#) and [Table 12](#).

Complete Response (CR) – disappearance of all *target* and *non-target* lesions and normalization of tumor markers. Pathological lymph nodes must have short axis measures <10 mm (*Note: continue to record the measurement even if <10 mm and considered CR*). Tumor markers must have normalized. Residual lesions (other than nodes <10 mm) thought to be non-malignant should be further investigated (by cytology or PET scans) before CR can be accepted.

Partial Response (PR) – at least a 30% decrease in the sum of measures (longest diameter for tumor lesions and short axis measure for nodes) of target lesions, taking as reference the baseline sum of diameters. Non-target lesions must be non-PD.

Stable Disease (SD) – neither sufficient shrinkage to qualify for PR nor sufficient increase to qualify for PD taking as reference the smallest sum of diameters on study.

Progressive Disease (PD) – at least a 20% increase in the sum of diameters of measured lesions taking as references the smallest sum of diameters recorded on study (including baseline) AND an absolute increase of ≥ 5 mm. Appearance of new lesions will also constitute PD (including lesions in previously unassessed areas). In exceptional circumstances, unequivocal progression of non-target disease may be accepted as evidence of disease progression, where the overall tumor burden has increased sufficiently to merit discontinuation of treatment, for example where the tumor burden appears to have increased by at least 73% in volume (which is the increase in volume when all dimensions of a single lesion increase by 20%). Modest increases in the size of one or more non-target lesions are NOT considered unequivocal progression. If the evidence of PD is equivocal (target or non-target), treatment may continue until the next assessment, but on further documentation, the earlier date must be used.

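### Section 6.2.1 and the synopsis let a biopsied lesion be one of several RECIST target lesions, while section 6.2.5.1 keeps biopsied lesions out of the RECIST assessment

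*Protocol*

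**What the plan says.** Three places in the protocol bear on whether a biopsied lesion may be measured for response.

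- **Section 6.2.1**, repeated in the synopsis under tumor biopsy, asks for a lesion suited to sequential biopsy, or one close by, and adds that "this lesion should ideally not be the only target lesion" followed on imaging in the study.
- **Section 6.2.5.1**, on tumor assessments: "Lesions that are being biopsied should not be included in the RECIST assessment".
- **Section 3.1, inclusion criterion 8** (Part B only), requires at least one non-irradiated lesion "accurately measured at baseline as ≥ 10 mm in the longest diameter" and says of it: "This shall not be the lesion that is going to be biopsied". The synopsis repeats this criterion. The opening of section 3 allows no exceptions to the eligibility criteria.

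Appendix 1 (A 1.1) takes as targets all measurable lesions up to five in total and two per organ, chosen by size, by how well they represent the involved organs and by reproducibility of measurement. It says nothing about biopsied lesions. Partial response is "at least a 30% decrease in the sum of measures" of the target lesions. Tumor shrinkage, confirmed PR or CR, and ORR by RECIST 1.1 are Part B primary endpoints (section 1.10.1).

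**The concern.** The choice of target lesions is fixed at baseline and decides which diameters enter the sum behind the Part B primary endpoint. Sections 6.2.1 and 6.2.5.1 give different answers for a biopsied lesion. A site working from the biopsy section may include it as one of several targets; a site working from the tumor assessment section leaves it out. Central reading is done post hoc in addition to local reading, so the two readers could also work from different target sets.

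A biopsied target lesion can change size for reasons other than treatment. Removed tissue can look like shrinkage, and bleeding or inflammation can look like growth. Exposure is greatest where an on-treatment biopsy is mandatory: melanoma, CSCC and the basket cohort. In CSCC, ideally 3 to 5 punch biopsies are taken at one timepoint, and cutaneous target lesions are measured by caliper (section 6.2.5.2).

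**Working it through.** The plan states no figure on this point, so the check compares the text and then adds simple arithmetic.

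**1. Do the rules conflict?**

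| Biopsied lesion is | 6.2.1 and synopsis, tumor biopsy | 6.2.5.1 | Inclusion criterion 8 (Part B) |
|---|---|---|---|
| one of several targets | allowed | should be left out | allowed, provided another measurable lesion is not biopsied |
| the only target | discouraged, not excluded | should be left out | barred |

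The first row is a direct conflict between 6.2.1 and 6.2.5.1 that criterion 8 does not resolve, because it protects one qualifying lesion only. Appendix 1 does not resolve it either: selection by size can bring a large biopsied lesion into the sum. The second row is closed in Part B by criterion 8.

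**2. Can biopsy fall between the scans being compared?** Yes. Inclusion criterion 7 says: "All other study eligibility criteria must be met before the baseline biopsy sample is obtained". Measurable disease is one of those criteria, so a fresh baseline biopsy can follow the baseline measurement. The on-treatment biopsy is due after 8 weeks (9 weeks in CSCC) and therefore precedes the later scans, including those that could confirm a response.

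**3. How large would the effect have to be?** Inputs: the 30% PR threshold and the PD threshold of at least 20% and at least 5 mm (Appendix 1), and the 10 mm minimum (criterion 8). Assumptions: the biopsied lesion measures *b* = 20 mm or 10 mm; the protected lesion is at the minimum, *s* = 10 mm, is also a target and does not change; there are no other targets; and baseline is the smallest sum.

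Loss needed for a 30% fall = 0.30 × (*b* + *s*).

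- *b* = 20: 0.30 × 30 = 9 mm, which is 9/20 = 45% of that lesion's diameter.
- *b* = 10: 0.30 × 20 = 6 mm, which is 6/10 = 60% of that lesion's diameter.

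Growth needed for PD = the larger of 0.20 × (*b* + *s*) and 5 mm.

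- *b* = 20: 0.20 × 30 = 6 mm.
- *b* = 10: 0.20 × 20 = 4 mm, so the 5 mm floor applies.

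More or larger targets raise these amounts. Genuine shrinkage elsewhere in the sum lowers the loss needed for PR, millimetre for millimetre.

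**The case against.** The strongest reply is that the protocol already has the right rule in the right place. Section 6.2.5.1 governs measurement, section 6.2.1 governs biopsy, and a reader measuring response would turn to the former. Criterion 8, with no exceptions, adds a guaranteed non-biopsied lesion in Part B. Section 6.2.1 also covers Part A, where enrolment is complete and efficacy is secondary. Archived baseline tissue taken before the baseline scan cannot produce shrinkage from that scan. Bladder, hepatocellular and lung cohorts have no mandatory on-treatment biopsy.

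Most of this stands and limits the point. It does not remove it: 6.2.1 expressly contemplates the biopsied lesion as a target, nothing ranks one section above the other, and the synopsis carries the sentence of 6.2.1 without the exclusion of 6.2.5.1.

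A reader might infer that a biopsied lesion can be the sole target in Part B, so that a loss of 3 mm from a 10 mm lesion (0.30 × 10) or 6 mm from a 20 mm lesion (0.30 × 20) would make a false response. Criterion 8 bars that case. A reader might also infer that criterion 8 forbids every biopsied target; it protects one lesion only, and the general exclusion in 6.2.5.1 is worded as a recommendation.

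**Conclusion.** The contradiction is certain: two sections give different rules on whether a biopsied lesion may enter the target sum in Part B. Its effect on tumor shrinkage, ORR or PD is possible but unknown in size, and it could go in either direction. Under the assumed sizes, a false PR from biopsy alone needs a loss of 9 mm (20 mm lesion) or 6 mm (10 mm lesion). The documents give no lesion sizes beyond the 10 mm minimum and no tissue loss per biopsy.

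A reader might go further and infer that expansion decisions will be tipped, because continuation needs as few as 1 responder in 14, or 2 in 12 for CSCC. The documents do not support that as a finding. They give no rate of biopsy-related misreading, and the Safety Review Committee and sponsor also weigh depth of response and safety before expanding a cohort. The correction is still worth making, because the rule decides what is measured for a primary endpoint and costs little to settle.

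**What to change.** In section 6.2.1 and in the tumor biopsy part of the synopsis, replace the sentence on the only target lesion with the rule of 6.2.5.1, for example: *Lesions that are biopsied should not be selected as target lesions and do not enter the RECIST assessment (see 6.2.5.1).* State that the rule applies to both local and central reading.

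The cost is one sentence in two places. The downside is small: in some subjects fewer lesions will be available as targets. Part B eligibility is unaffected, since criterion 8 already requires a measurable lesion that is not biopsied.

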6.2.2. Demographics and Medical History

Demographics (age, sex, race/ethnicity [if allowed per country-specific regulations]) and height will be recorded along with a full review of medical history including cancer history (e.g., prior therapies including radiation and surgery) and known tumor biology (e.g., historical data for PD-L1). All relevant medical history of all body systems and history of all prior therapies for cancer and other relevant therapies will be collected and recorded in the eCRF.

6.2.3. Assessment of Weight

At Screening, weight will be assessed and data on weight 6 months prior to Screening, if available, or any data until Screening, as available, will be recorded. Thereafter, weight will be assessed every 2 weeks for Part A (see [Table 5](#)), every 2 weeks for Part B combination therapy with nivolumab (see [Table 6](#)) and every 3 weeks for Part B combination with cemiplimab ([Table 7](#)) and at End of Treatment Visit (see [Section 6.1.9](#)).

6.2.4. Assessment of Safety

The safety and tolerability of IV infusions of CTL-002 monotherapy and CTL-002 in combination with the defined checkpoint inhibitor will be evaluated by the incidence of AEs (all AEs will be evaluated according to NCI-CTCAE v5.0), SAEs, DLTs, and use of concomitant medications. Safety assessments will include: ECGs, physical examinations including neurological examination (motor neuropathy can be conducted by any treating physician, no neurology board certification required), ECOG performance status, vital signs and clinical laboratory samples (hematology, clinical chemistry, coagulation, thyroid function (thyroid stimulating hormone [TSH] and free T3), cytokines, assessment of HbA1c, NT-proBNP, and urinalysis).

Subjects are assessed for safety at Screening, as well as during treatment until the Safety Follow-up Visit. Thereafter safety related to the study is further captured during the follow-up of up to 12 months (Part A)/24 months (Part B) post-treatment. Planned time points for all safety assessments are provided the SoAs in [Table 5](#), [Table 6](#) and [Table 7](#).

6.2.4.1. Vital Signs

Vital signs including systolic and diastolic BP (sitting), pulse rate, temperature, respiratory rate, and oxygen saturation should be evaluated at Screening and at the time points indicated in the SoAs in [Table 5](#), [Table 6](#) and [Table 7](#). Additional vital sign measurements may be performed if clinically warranted.

6.2.4.2. Physical and Neurologic Examination

A physical examination will be performed at Screening and will include examination of head, eyes, ears, nose, throat, neck, cardiovascular, chest/lungs, abdomen (including liver and spleen size), extremities, skin, and lymph nodes, as well as a brief neurologic examination to assess motor neuropathy (motor neuropathy examination can be conducted by any treating physician, no neurology board certification required).

Additional physical examination assessment time points are outlined below and in the SoAs in [Table 5](#), [Table 6](#) and [Table 7](#).

6.2.4.3. Performance Status

Performance status will be assessed at Screening and at the time points in the SoAs in [Table 5](#), [Table 6](#) and [Table 7](#) according to ECOG criteria as follows:

- 0 = Fully active, able to carry out all pre-disease activities without restrictions
- 1 = Restricted in physically strenuous activity but ambulatory and able to carry out work of a light or sedentary nature (e.g., light housework, office work)
- 2 = Ambulatory and capable of self-care, but unable to carry out any work activities. Up and about more than 50% of waking hours
- 3 = Capable of only limited self-care, confined to bed or chair more than 50% of waking hours
- 4 = Completely disabled, cannot carry on self-care, totally confined to bed or chair
- 5 =Death

